#### Objective 4:

NOMAC and CMA will be assessed separately. Covariates for stratification will include:

- Dose
- Indication
- Time period

#### Objective 5:

NOMAC and CMA will be assessed separately. Covariates for stratification will include:

- WHO 5th ATC level codes
- Time period

#### Objective 6:

NOMAC and CMA will be assessed separately. Covariates for stratification will include:

- Dose
- Indication

Please see the "11 Limitations" for important information on these covariates.

## **Covariates for Objective 3 (characterisation):**

For objective 3, pre-specified comorbidities and comedications will be reported. Pre-specified comorbidities will include meningioma and conditions that might play a role in modifying its risk.(12, 13) Potential indications of these drug classes of interest will also be considered, including gynaecological disorders and menopause.

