## Covariates for stratification:

- Age group: 10-17, 18-34, 35-49, 50-64, +65 years (Objective 1)
- Dose: High- vs. low- dose, for NOMAC and CMA only (Objective 1,4,6)
- Indication: HRT (hormonal replacement therapy) vs. non-HRT, with age as a proxy (Objective 1,2,4,6)
- WHO ATC 5th level code: For NOMAC and CMA only (Objective 1 and 5).
- Study period: Pre- vs. Postintervention (Objective 1 to 5).

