#### Objective 2 to 5:

Standardised mean differences of each of the covariates for the comparison of drug users in the pre-RMM and post-RMM period as a measure of the impact of the profile of drug users. These covariates will include: duration and cumulative dose (objective 2), patient characteristics in terms of prior comorbidities (objective 3) and line of treatment (objective 4). For objective 5, these will include the proportion of patients discontinuing orswitching treatments (assessed separately), and the proportion of patients diagnosed with meningioma during treatment.

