#### Objective 3:

Characteristics will be described by means of large-scale characterisation. The top 10 of disease codes and top 10 of drug codes will be described in the report to simplify dissemination. Pre-specified comorbidities and concomitant medications will also be reported within specific time windows (see "8.6.3. Other covariates"). The number of patients initiating high- or low-doses of NOMAC and CMA (assessed separately) and the number of years since meningioma diagnosis will also be described.

Results will be reported overall and stratified by study period (pre- vs. postintervention).

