#### Objective 2-5:

For objectives 2 to 5, SMD of each of the covariates for the comparison of drug users in the pre-RMM and post-RMM period as a measure of the impact of the profile of drug users. These covariates will include: duration and cumulative dose (objective 2), patient characteristics (objective 3) and line of treatment (objective 4). For patient characteristics, only conditions will be compared, with the assessment window set as any time prior to 1 day before the index date. For objective 5, covariates will include the proportion of patients diagnosed with meningioma during treatment, and the proportion of patients who discontinue or switch to alternative treatments (assessed separately).

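### Objective 3 leaves age at first prescription out of the pre/post comparison, so age-driven movement in the condition SMDs cannot be recognised

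*Protocol*

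**What the plan says.** Section 8.6.3 (Covariates for Objective 3) opens with "For objective 3, pre-specified comorbidities and comedications will be reported". It then lists conditions and drugs; age is in neither list. Section 8.8, Objective 3, adds large-scale characterisation, numbers starting high or low dose, and years since a meningioma diagnosis. On the large-scale output it says: "The top 10 of disease codes and top 10 of drug codes will be described in the report to simplify dissemination". Sections 8.6.3 and 8.8 both stratify Objective 3 by study period only.

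Section 8.8, Objective 2-5, restricts the comparison: "For patient characteristics, only conditions will be compared, with the assessment window set as any time prior to 1 day before the index date". The same paragraph presents the SMDs "as a measure of the impact of the profile of drug users". The abstract agrees, limiting the Objective 3 comparison to prior comorbidities.

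Age group is assigned to Objective 1 in the abstract, and to the general population of Objectives 1 and 6 in Table 9. The age-50 proxy for indication is used in Objectives 1, 2, 4 and 6, but not in 3.

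**The concern.** Objective 3 is meant to show whether the kind of woman starting treatment changed after the 2022 measures. Several of the compared conditions become much more common with age. If the age mix of starters differs between periods, all of these SMDs move in the same direction, even when prescribers choose among women of a given age exactly as before.

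There are two routes. The first is secular: the pre-period is long, the post-period is short, and Objective 3 has no matched window such as Objective 2 has. The second is the measures themselves: high-dose products lost first-line status, while section 6 places contraceptive use at lower doses, so a shift towards younger starters is plausible. With age in neither the listed output nor the SMDs, a reader cannot separate either route from a change in selection by comorbidity.

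**Working it through.** The protocol gives no SMD threshold, precision figure or expected difference for Objective 3, so there is no planned figure to reproduce. The check has three parts.

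**1. Period lengths (section 8.6.3, section 11, Table 3)**

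- Pre-period, to October 2022. Germany from January 2010: 154 months / 12 = 12.8 years. Belgium from 2012: 130 / 12 = 10.8 years. Croatia from 2017: 70 / 12 = 5.8 years.
- Post-period, from February 2023 to the data lock. Germany (30 September 2023): 8 months. Croatia (17 November 2023): about 9.5 months. Belgium (31 December 2023): 11 months.

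**2. Effect of age mix alone (all inputs assumed)**

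Let s be the share of starters aged 50 or over, with prevalence fixed within each age stratum:

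- p = s × p(50+) + (1 - s) × p(<50)
- SMD = (p_post - p_pre) / sqrt{[p_pre(1 - p_pre) + p_post(1 - p_post)] / 2}

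Example: s falls from 40% to 25%, with prevalence 5% under 50 and 35% from 50 on.

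- p_pre = 0.40 × 0.35 + 0.60 × 0.05 = 0.170
- p_post = 0.25 × 0.35 + 0.75 × 0.05 = 0.125
- SMD = -0.045 / sqrt[(0.1411 + 0.1094) / 2] = -0.13

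For a menopause record at 5% and 60%, p goes from 0.270 to 0.1875, SMD -0.20. If s falls from 30% to 15%, the two SMDs are -0.14 and -0.22.

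Further cases (prevalence under 50 / 50 or over):

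| s pre → post | Age 50+ itself | Hypertension-like (5% / 35%) | Menopause-like (3% / 40%) | Asthma-like (8% / 9%) |
|---|---|---|---|---|
| 40% → 30% | -0.21 | -0.08 | -0.10 | 0.00 |
| 40% → 20% | -0.45 | -0.17 | -0.21 | -0.01 |
| 15% → 13% | -0.06 | -0.02 | -0.03 | 0.00 |
| 15% → 5% | -0.34 | -0.11 | -0.15 | 0.00 |

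Age-related conditions move together and age-neutral ones stay still. An age shift upwards would reverse the signs.

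**3. Which cohort (measures-driven route only)**

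The abstract's exposure list defines Objective 3 by a first prescription of NOMAC or CMA, assessed separately. Table 1, section 8.4, Table 4, section 8.6.1 and Table 7 define it by a first prescription of any class of interest, with one washout across all classes.

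Assume that 70% of high-dose starters and 15% of all others are aged 50 or over, that 20% to 40% of NOMAC/CMA starters are high-dose, and that half or all of high-dose initiation is lost. For the hypertension-like condition:

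- NOMAC/CMA-only cohort: SMD -0.045 to -0.199. Upper case: s falls from 0.37 to 0.15, so p goes from 0.161 to 0.095.
- Pooled cohort with NOMAC/CMA at 5% to 20% of starters: SMD -0.003 to -0.044. Upper case: s falls from 0.194 to 0.15, so p goes from 0.108 to 0.095.

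Together with the menopause example in part 2, the NOMAC/CMA-only range is about -0.05 to -0.22.

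**The case against.** **Age is visible elsewhere.** Objective 1 gives incidence for each class, NOMAC and CMA by age group, indication, dose and period, and Objectives 2 and 4 split NOMAC and CMA starters at age 50. This helps, but Objective 1 follows another cohort: 365-day washout, multiple entry and one substance or class at a time, against lifetime washout, single entry and all classes combined. Objective 1 also drops the last six months in Germany and Belgium. At the Table 3 lock, Germany keeps only February and March 2023 after the measures. These results cannot be laid over the Objective 3 SMDs.

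**Table rows are analysis-plan detail.** This partly stands. The list of conditions and drugs does not forbid an age row, and the last column of Table 9 is not exhaustive: it also confines indication to the general population, although Objectives 2 and 4 use it. The restriction of the SMDs to conditions, however, is fixed in the protocol.

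**An age shift caused by the measures is a real effect.** This stands. Age would then be a mediator, and fewer older starters is part of the changed user profile. A reader might infer that the condition SMDs are spurious or wrongly credited to the measures. The protocol does not support that: Objective 3 is descriptive, and nowhere does it define the SMD as selection within age. The defect is that the sources of change cannot be told apart.

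**The high-dose restriction is not shown to change the age mix.** This also stands. No section gives age by dose, and section 6 lists gynaecological and menstrual disorders without tying them to an age.

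**Conclusion.** The omission is established: age is not a listed characteristic for Objective 3, and the pre/post SMDs are closed to it. As a result, SMDs for age-dependent conditions cannot be interpreted with confidence across periods of such unequal length.

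Direction and size are not established. A reader might take SMDs of -0.13 to -0.22 as the expected distortion. Those values rest on assumed age shares and prevalences, and as an effect of the measures they fit only a NOMAC/CMA-only cohort. In the pooled cohort that most of the protocol defines, the assumed effect of losing high-dose starters is at most about -0.044. Secular drift in age does not depend on the NOMAC/CMA share and could matter in either cohort, but the protocol has no data on it.

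Severity is minor to moderate: a cheap improvement to a descriptive objective, plus a conflict in the cohort definition that must be settled before the results can be read.

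**What to change.** - Add age at index date to the Objective 3 table by study period: median, interquartile range and the five existing age groups.
- Include age in the pre/post SMDs. In section 8.8, Objective 2-5, let the comparison cover *age and conditions*.
- As a supporting descriptive table, show the condition SMDs under 50 and 50 or over where counts allow.
- Reconcile the abstract's exposure list with Table 1, section 8.4, Table 4, section 8.6.1 and Table 7 on who forms the Objective 3 cohort.

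The cost is small. Age is already needed in every database for Objectives 1, 2, 4 and 6. The additions are one variable and one table, and some age-specific cells will fall below the minimum count of 5. The change does not deal with other differences between the periods, such as longer recorded history after 2022 when conditions are counted at any earlier time.

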#### **Comorbidities of interest:**

Relevant conditions considering the restrictions of use:

- Meningioma

Comorbidities that might play a role in meningioma risk:

- Type 2 neurofibromatosis (1)
- Obesity (14, 15)
- Diabetes mellitus (16)
- Autoimmune diseases (17, 18)
- Asthma (17-19)
- Epilepsy (17)
- Uterine fibroids (13)

Potential indications for drug classes of interest:

- Menopause / Perimenopause
- Primary ovarian insufficiency
- Endometriosis
- Polycystic ovary syndrome
- Menstrual disorders

Authors: [name], [name], [name], [name], [name]

Version: V4.0

Dissemination level: Public

- Neoplasm of endometrium

#### Other comorbidities:

- Hyperlipidaemia
- Hypertensive disorder
- Osteoporosis
- Neoplasm of the brain
- Neoplasm of the breast
- Cancer (any malignancy)
- Venous thromboembolism

Pre-specified concomitant medications will consist of the drug classes of interest included in this study.

#### **Medications of interest:**

#### Drug classes of interest:

- Progestogen and oestrogen combination products not including NOMAC or CMA.
- Progestogens that are pregnadien derivates not including NOMAC or CMA.
- NOMAC (high- and low-dose products, assessed separately)
- CMA (high- and low-dose products, assessed separately)
- Medroxyprogesterone

Drugs used in the management of conditions for which medications of interest might be prescribed:

- Antidepressants
- Antihyperglycemics (Metformin)
- Bisphosphonates
- Clonidine
- Gonadotropin Releasing Hormone antagonists
- Anti-androgens (bicalutamide, flutamide, finasteride, spirolactone, cyproterone acetate)

A preliminary list of concepts to identify pre-specified comorbidities and comedications is detailed in the **Appendix I**. Comorbidities will be measured for any time prior to 1 day before index date, 365 days prior to 1 day before index date and at index date. Concomitant medications will be described 365 days prior to 31 days before index date, and 30 days to 1 day before index date, and at index date.

The operational definition of the covariates is described in the Table 9.

Authors: [name], [name], [name], [name], [name]

Version: V4.0

Dissemination level: Public

**Table 9.** Operational definitions of covariates.

Characteristic	Details	Type of variable	Assessment window	Care Setti ngs 	Code Type	Diagn osis Positi on 	Applied to study populations
Age groups	Defined as: 10-17, 18-34, 35-49, 50-64, +65.	Categorical	N/A	IP, OP	N/A	N/A	General population (objective 1 and 6)
Dose (NOMAC and CMA)	High vs. low doses. For NOMAC, high doses will include amounts from 3.75mg to 5mg. For CMA, high doses will include amounts from 5mg to 10mg. Low doses will be any amounts less than those specified.	Categorical	0	IP, OP	N/A	N/A	General population (objective 1 and 6)
Indication	Non-HRT vs. HRT. Age will be used as a proxy (non-HRT in women aged 10-49 years, HRT in women aged >50 years).	Categorical	0	IP, OP	N/A	N/A	General population (objective 1 and 6)
Comorbidities	Large-scale characterisation and pre-specified conditions 	Binary	[-Inf, -1], [- 365,-1], 0	IP, OP	SNO MED	Any	New users of drug classes or progestogens of interest (objective 3)
Concomitant medications	Large-scale characterisation and pre-specified medications 	Binary	[-365, -31], [-30,-1], 0	IP, OP	RxNo rm		New users of drug classes of interest or progestogens (objective 3)
Time period	Preintervention: January 2010 (or study start) to October 2022 Postintervention: February 2023 to end of available data	Categorical	N/A	IP, OP	N/A	N/A	All.

<sup>1IP = inpatient, OP = outpatient

## 8.7 Study size

The expected number of patients exposed to NOMAC or CMA is expected to be roughly between 1,900 in NAJS and 16,800 in IQVIA DA Germany and between 2,4004 in IQVIA LPD Belgium and 173,900 in IQVIA

<sup>2Specify whether a diagnosis code is required to be in the primary position (main reason for encounter)

<sup>3 These will include: meningioma, obesity, diabetes mellitus, type 2 neurofibromatosis, asthma, autoimmune diseases, epilepsy, uterine fibroids, menopause/perimenopause, primary ovarian insufficiency, endometriosis, polycystic ovarian syndrome, menstrual disorders, neoplasm of the endometrium, neoplasm of the brain, neoplasm of the breast, cancer (any malignancy), hyperlipidaemia, hypertensive disorder, osteoporosis, venous thromboembolism.

<sup>4 These will include: progestogen and oestrogen combination products not containing NOMAC or CMA, progestogens that are pregnadien derivates not containing NOMAC or CMA, progestogen and oestrogen combination products not containing NOMAC or CMA, NOMAC, CMA, medroxyprogesterone, antidepressants, metformin, bisphosphonates, clonidine, gonadotropin releasing hormone antagonists and anti-androgens.

Authors: [name], [name], [name], [name], [name]

Version: V4.0

**Dissemination level:** Public

DA Germany, respectively. These counts were provided as part of the feasibility assessment and correspond to the entire source data, without restriction on age, sex or study period.

No specific sample size calculations have been performed. Given that meningioma is a rare tumour, we expect to have limited sample size in Objective 1, when restricting the population to individuals with prior history of meningioma. For Objective 3, 4 and 5, we expect an adequately large sample size to estimate Standardised Mean Differences (SMD) accurately. For Objective 2, this might be more limited as we will only consider users initiating treatment within a period of 6 to 12 months.

Several factors have been identified to potentially influence the power to estimate the impact of the intervention, including the total number of time points, the average sample size per time point, the expected effect size, the location of intervention in time series or the impact model used.(20) In previous studies, ITS have been found to have more than 80% power to detect effect sizes of 1.0 or greater in a range of situations with 24 or more points, depending on the degree of autocorrelation and the impact model used.(21) Unbalanced designs (i.e. unequal number of time points before and after the intervention) have been found to have less power than balanced designs.(20, 21) As the intervention is located at the end of the time series, we will delay the study period start to balance the number of observations for Objective 6 and to ensure a more recent contrafactual for comparison (see "8.8 Analysis").

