**Dissemination level: Public** 

Country	Name of Database 	Justification for Inclusion	Health Care setting 	Type of Data 	Number of active subjects 	Feasibility count of NOMAC 	Feasibility count of CMA 	Data lock for the last update
Croatia	NAJS	Suitable denominator population for population for population-level rates.  Follow-up data up to 1 year after the implementation of restrictions of use.  Observed records of individuals exposed to nomegestrol and chlormadinone.  Contribute to the geographical diversity of data sources.	Primary care, hospital care (IP, OP)	Registry	2.68M	1.9k	15.3k	17-11-2023

- 1. IQVIA DA= IQVIA Disease Analyzer; IQVIA LPD= IQVIA Longitudinal Patient Database; NAJS= Croatian National Public Health Information System
- 2. IP= inpatient, OP= outpatient.
- 3. EHR = Electronic health records
- 4. Defined as the maximum number of persons in an observation period in the last 6 month
- 5. Person counts provided as part of the feasibility assessment using preliminary concepts. Counts correspond to the whole database, without restriction on age, sex or study period. All counts are rounded to the nearest multiple of 100. NOMAC= Nomegestrol acetat; CMA = Chlormadinone acetate.

Authors: [name], [name], [name], [name], [name]

Version: V4.0

Dissemination level: Public

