#### A. Primary analysis

Hypothesis:	Objective 1: Not applicable, descriptive analysis.
	Objective 2: Cumulative dose and duration of treatments with NOMAC or CMA will be lower after the implementation of restrictions.
	Objective 3: The number of new users of NOMAC or CMA with prior history of meningioma will be reduced after the implementation of restrictions.
	Objective 4: The number of users initiating NOMAC or CMA as first-line treatment will be reduced after the implementation of restrictions.
	Objective 5: The number of discontinuations and switches from NOMAC or CMA to other drug classes will increase after the implementation of restrictions.
	Objective 6: The incidence of NOMAC or CMA will be reduced after the implementation of restrictions, especially for high-dose products. This reduction will not be observed for other drug classes of interest.
Exposure contrast:	Objective 1: Not applicable, descriptive analysis.
	Objective 2: Pre-intervention (1-year period) vs. Post-intervention (1-year period)
	Objective 3 to 6: Pre-intervention vs. Post-intervention
Outcome:	Objective 1: Incidence rates and prevalence of drug classes of interest
	Objective 2: Cumulative dose and treatment duration of NOMAC or CMA.

Authors: [name], [name], [name], [name], [name]

Version: V4.0

Dissemination level: Public

	Objective 3: Number and characteristics of users of drug classes of interest.
	Objective 4: Line of treatment when initiating NOMAC or CMA.
	Objective 5: Diagnosis with meningioma during treatment. Discontinuations and switches
	from treatments with NOMAC or CMA to others.
	Objective 6: Incidence rates of NOMAC or CMA.
	Drug classes of interest, NOMAC and CMA will be assessed separately.
Analytic software:	R
Model(s):	Objective 1: Not applicable, descriptive analysis.
	Objective 2 to 5: Standardised mean differences.
	Objective 6: Segmented regression (Poisson models).
Confounding adjustment method	
	Stratification.
Missing data methods	
	The absence of a record for a condition or medication will be considered as the absence of the disease or use of the medication.
Subgroup Analyses	
	Objective 1: Age groups, indication, study period. For NOMAC or CMA only: dose, WHO ATC 5 th level (if counts allow). A subgroup analysis will be performed restricting the study population to individuals with a prior history of meningioma.
	Objective 2: Study population, indication, study period.
	Objective 3: Study period.

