#### Analysis:

Due to the limited number of feasibility counts for meningioma (in the order of hundreds across most databases), studying the effect of the restrictions of use among this population will not be feasible. A subgroup analysis for this population has been included for Objective 1 for descriptive purposes; however, it is unlikely to have a sufficient number of patients to allow for formal analysis.

The dates of the interventions were determined based on EU-level restrictions. However, we excluded the restrictions imposed in 2020 on products containing NOMAC in combination with oestradiol (see the introduction for further details). The rationale for this exclusion is that the 2020 intervention is likely to have been affected by the coronavirus disease (COVID-19) pandemic. Including this restriction could result in biased estimates, as any observed effects might be attributed to the pandemic rather than the intervention itself. The effect of the COVID-19 pandemic might still be seen in 2021, which will affect the ability to capture stable trends for Objective 6. Methodological considerations for Objective 6 will be thoroughly evaluated based on the visual assessment of the trends. Regarding the timing of interventions, some countries may have implemented national-level measures prior to the EU restrictions. These measures fall outside the scope of this study and will be considered for context and interpretation only.

The amount of current available data might not fully capture the long-term effects resulting from the RMM implemented in November 2022. Further studies using additional follow-up data (once available) might be needed to assess the long-term impact of the intervention.

Segmented regression (Objective 6) might not be appropriate if trends cannot be transformed to be linear or if there is residual autocorrelation. Other modelling approaches such as Autoregressive Integrated Moving Average (ARIMA) models could be considered. However, these methods require a substantial number of time points before and after the intervention and are not feasible given the currently available post-intervention data.

Authors: [name], [name], [name], [name], [name]

Version: V4.0

Dissemination level: Public

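### Section 8.7 calls the sample adequate for accurate SMDs in Objectives 3 to 5 on the strength of whole-database ever-user counts, which does not hold for the smallest Objective 4 cohorts or the meningioma-history comparison

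*Protocol*

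**What the plan says.** Section 8.7 reports that "No specific sample size calculations have been performed". It gives expected exposed patients as "roughly between 1,900 in NAJS and 16,800 in IQVIA DA Germany and between 2,4004 in IQVIA LPD Belgium and 173,900 in IQVIA" DA Germany and says that these counts "correspond to the entire source data, without restriction on age, sex or study period". Table 3 has the six counts by substance and database; its 2.4k for chlormadinone (CMA) in Belgium shows that 2,4004 is a misprint.

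Section 8.7 then concludes: "For Objective 3, 4 and 5, we expect an adequately large sample size to estimate Standardised Mean Differences (SMD) accurately". In the same paragraph it expects limited numbers for the Objective 1 meningioma subgroup, and for Objective 2 because only users starting within 6 to 12 months count.

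Related provisions:
- Table 4 defines one set of nomegestrol (NOMAC) and CMA new-user cohorts for Objectives 2, 4 and 5.
- Section 8.6.3 starts the post-intervention period in February 2023. The Table 3 locks are 30 September 2023 (Germany), 31 December 2023 (Belgium) and 17 November 2023 (NAJS, described as "Follow-up data up to 1 year after the implementation of restrictions of use").
- Table 11 gives the Objective 3 hypothesis as "The number of new users of NOMAC or CMA with prior history of meningioma will be reduced after the implementation of restrictions". Section 8.8 lists among the Objective 5 SMDs "the proportion of patients diagnosed with meningioma during treatment".
- Section 11 opens its analysis limitations with "Due to the limited number of feasibility counts for meningioma (in the order of hundreds across most databases") and concludes that the effect of the restrictions cannot feasibly be studied in that population.
- Results are produced per database without meta-analysis, and counts below five are masked (sections 8.8 and 8.9).

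**The concern.** The sampling error of a pre/post SMD is governed by the smaller group. Here that is the set of women starting treatment after January 2023, and a long pre-period adds little. The counts in section 8.7 do not describe that group. The reason given for caution in Objective 2, a short initiation window, applies equally to the post arm of Objective 4, which is drawn from the same cohorts.

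The adequacy sentence also makes no exception for meningioma, although one hypothesis and one planned SMD concern it and section 11 says the numbers are too few for an effect analysis.

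Two conclusions are at stake. In the smallest pairs, an SMD printed without an interval may be read as a change in line of treatment when it is within sampling error. For meningioma history, a post-period cell shown as under five would usually look the same whether or not the measures worked.

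**Working it through.** Section 8.7 gives no precision figure, so there is none to reproduce.

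**Inputs.** Counts, active subjects and locks are from Table 3; start dates are from sections 8.3 and 11 (Germany 2010, Belgium 2012, NAJS 2017); the pre-period ends in October 2022 and the post-period starts in February 2023. In months, pre / post / total: Germany 154 / 8 / 165; Belgium 130 / 11 / 144; NAJS 70 / 9.57 / 82.57.

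**Assumption 1.** All counted users start within the study period at an even rate.

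**Formulas.** n_post = count × post months / total months, and likewise n_pre. The 95% half-width of an SMD near zero is 1.96 × √(1/n_pre + 1/n_post).

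Belgium CMA: n_post = 2,400 × 11/144 = 183; n_pre = 2,400 × 130/144 = 2,167; half-width = 1.96 × √(1/2,167 + 1/183) = 0.151.

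NAJS NOMAC: n_post = 1,900 × 9.57/82.57 = 220; n_pre = 1,900 × 70/82.57 = 1,611; half-width = 0.141.

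| Pair | n_pre | n_post | Half-width |
|---|---|---|---|
| Belgium CMA | 2,167 | 183 | 0.151 |
| NAJS NOMAC | 1,611 | 220 | 0.141 |
| Belgium NOMAC | 6,049 | 512 | 0.090 |
| Germany NOMAC | 15,680 | 815 | 0.070 |
| NAJS CMA | 12,971 | 1,773 | 0.050 |
| Germany CMA | 162,307 | 8,432 | 0.022 |

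**Sensitivity of the two smallest pairs.**

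| Scenario | Belgium CMA | NAJS NOMAC |
|---|---|---|
| First year lost to the 365-day history rule, same count spread over the rest | 0.145 | 0.132 |
| Post-period uptake 1.5 times the average | 0.128 | 0.122 |
| Post-period uptake halved | 0.205 | 0.187 |
| Half-size dose or indication stratum, even uptake | 0.21 | 0.20 |

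The stratum row is 1.96 × √(1/1,083 + 1/92) and 1.96 × √(1/805 + 1/110). If uptake halves, Belgium NOMAC also widens, to 0.123. To reach ±0.10, about 481 of 2,400 users (20%) in Belgium CMA, or 535 of 1,900 (28%) in NAJS NOMAC, would have to start in the post window. That window is 7.6% (11/144) and 11.6% (9.57/82.57) of the study period.

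**Meningioma history.** Assumption 2: 100 to 999 cases per database, as a reading of the order of hundreds in section 11, divided by active subjects. Expected post-period starters with prior meningioma = n_post × cases / active subjects.

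- Belgium NOMAC, highest: 512 × 999/213,000 = 2.4.
- Germany CMA, upper end: 8,432 × 999/4,350,000 = 1.9.
- NAJS NOMAC, lowest: 220 × 100/2,680,000 = 0.01.

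If all cases are women and women are half the database, these double, to at most 4.8. Conversely, if Belgian cases are set against the 1.1 million cumulative patients of section 8.2, the Belgium NOMAC maximum falls to 0.46.

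At an expectation of 2.4, no cases at all would occur by chance with Poisson probability e^(−2.4) = 0.09, so even complete disappearance would not be clearly distinguishable from no effect.

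**The case against.** The strongest reply is that the protocol does not itself supply these figures. It gives ever-user counts and an order of magnitude for meningioma; uptake and prevalence are assumed above. That stands. A reader might infer that the protocol's own counts yield fewer than five meningioma-related users and half-widths of at least ±0.14. They do not: ±0.14 is not a floor, as the 1.5-times scenario shows.

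A reader might also infer that the adequacy statement fails for Objectives 3 to 5 as a whole. The documents do not support this. The half-widths apply directly only to Objective 4. The body of the protocol defines Objective 3 as new users of any drug class of interest (the abstract's exposure line is narrower), and Objective 5 counts prevalent as well as incident users in its period comparison. Neither population is counted, and both can be larger. For common covariates four of six pairs look reasonable, and the protocol sets no SMD cut-off or precision target against which ±0.14 would fail.

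Nor does it follow that a meningioma SMD cannot be computed. The half-width formula depends on group sizes and gives ±0.022 for Germany CMA. The difficulty is a contrast resting on a handful of events. In the extreme case of 4.8 expected, the Poisson chance of five or more is about 52%, so a masked cell is not certain.

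Two further points have some weight. The study runs to the end of available data and execution is planned for March/April 2025, so a later cut could lengthen the post window. And the section 11 limitation is written about the population with meningioma and its Objective 1 subgroup. It is consistent with the sparse-data problem here, but is not a direct contradiction of section 8.7. The misprint 2,4004 is clerical and changes nothing.

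**Conclusion.** The point holds in limited form. Section 8.7 states adequacy without a calculation and without reference to the post-period group. For Objective 4, on even uptake at the Table 3 locks, precision is about ±0.15 for Belgium CMA and ±0.14 for NAJS NOMAC. It is about ±0.12 to ±0.13 if uptake is 1.5 times the average, and about ±0.19 to ±0.21 if it halves or in half-size strata. The other four pairs are at ±0.09 or better on even uptake.

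The Table 11 hypothesis on meningioma history cannot be informatively assessed by a pre/post contrast within one database. Expected post-period NOMAC or CMA starters with prior meningioma are about 0.01 to 2.4 per pair, or up to 4.8 with the women-only doubling. The larger any-class cohort of Objective 3 does not help, because the hypothesis concerns NOMAC and CMA users.

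The SMD for meningioma during treatment is likely to be sparse too, but its size is not shown, because the number of prevalent users is not given. This is an overbroad study-size statement, worth correcting before results are interpreted.

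**What to change.** 1. In section 8.7, give expected post-period counts per substance and database at the actual data cut.
2. Limit the adequacy statement to common covariates in the larger pairs, and exclude the meningioma items explicitly.
3. In Table 11 and section 8.8, label the meningioma-history and meningioma-during-treatment comparisons as descriptive, reported as n/N with an exact 95% confidence interval where masking allows.
4. Report each SMD with its 95% confidence interval and both group sizes.
5. Correct 2,4004 to 2,400 in the abstract and section 8.7.

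The cost is a less favourable study-size statement and slightly larger tables. No further data are needed beyond counts by period.
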